8.6.3 Anti-Drug Antibodies

Results of the anti-drug antibodies (ADA) tests will be listed and the number of subjects with a confirmed positive sample will be summarized.

8.6.4 Clinical Laboratory Tests

For clinical laboratory parameters, descriptive summary tables for observed values and changes from baseline will be provided by visit.

Laboratory values will also be categorized according to their NCI-CTCAE version 5 toxicity grade, for the following parameters: ALT, AST, Bilirubin, Creatinine, Hemoglobin, Platelets, Neutrophils, and Lymphocytes. For applicable parameters, shift tables will be presented from the baseline toxicity grade to the worst post-baseline visit value (scheduled or unscheduled). All test results and associated normal ranges from local laboratories will be reported in SI units. All tests with numeric values will have a unique unit per test. Any laboratory test results and associated normal ranges from local laboratories will be converted to SI units. For the limited number of cases where the associated normal ranges from a local laboratory cannot be obtained despite due diligence, if query is unsuccessful at resolving issue and analysis is mandatory then the clinical scientist and medical monitor can provide a suitable normal range to be used in determining CTC grading and flags for above and below normal and the inferred normal range will be flagged in listings.

If a test value is reported with "<" or ">" sign (as below or above some detection limit), the test value will be imputed in summaries at the limit of detection (that is ignoring "<" or ">" signs), however the measurement will be listed as originally reported.

A standard 'eDISH' (evaluation of Drug-Induced Serious Hepatotoxicity) plot will be presented to display on the log-log scale the correlation between peak total bilirubin and alanine aminotransferase (ALT), both in multiples of ULN, with horizontal and vertical lines for Hy's law thresholds, i.e., 3×ULN for ALT and 2×ULN for total bilirubin.

Listing will be provided for Safety Analysis Set.

Confidential Page 25 of 30

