4.3.5 Endocrine irAEs

Rule out non-inflammatory causes. If non-inflammatory cause is identified, treat accordingly and continue therapy per protocol. Consider visual field testing, endocrinology consultation, and imaging (Table 7).

Confidential Page 42 of 78

Table 7: Endocrine ir AE Management Algorithm

	Endocrine irAEs										
Endocrine Disorder	Management	Follow-Up									
Asymptomatic TSH abnormality	 Continue AGEN1884 therapy per protocol. If TSH <0.5 x lower limit of normal (LLN) or TSH >2 x ULN, or consistently out of range in 2 subsequent measurements: Include free thyroxine (T4) at subsequent cycles as clinically indicated; consider endocrinology consult. 										
Symptomatic endocrinopathy	 Evaluate endocrine function. Consider pituitary scan. Symptomatic with abnormal lab/pituitary scan: Delay AGEN1884 therapy per protocol; 1-2 mg/kg/day methylprednisolone IV or oral equivalent; initiate appropriate hormone therapy. No abnormal lab/pituitary MRI scan but symptoms persist: Repeat labs in 1-3 weeks, MRI in 1 month. 	 If improves (with or without hormone replacement): Taper corticosteroids over ≥1 month and consider prophylactic antibiotics for opportunistic infections. Resume AGEN1884 therapy per protocol. Subjects with adrenal insufficiency may need to continue corticosteroids with mineralocorticoid component. 									
Suspicion of adrenal crisis (e.g., severe dehydration, hypotension, shock out of proportion to current illness)	 Delay or discontinue AGEN1884 therapy per protocol. Rule out sepsis. Stress dose of IV corticosteroids with mineralocorticoid activity. IV fluids. Consult endocrinologist. If adrenal crisis ruled out, treat as above for symptomatic endocrinopathy. 										

irAE: immune-related adverse event; IV: intravenous; kg: kilogram; LLN: lower limit of normal; mg: milligram; MRI: magnetic resonance imaging; TSH: thyroid stimulating hormone; ULN: upper limit of normal.

Confidential Page 43 of 78

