5.1 Schedule of Assessments

The schedule of assessments is provided in Table 10.

Confidential Page 47 of 78

Table 10: Schedule of Assessments

	Screening		Treatment and Evaluation								Disease Assessments	End of Treatment Visit	Final Safety Visit	Survival F/U	
Study Week		1	2	4		7		10		12	Q3, 6, and 12W after Week 12	After disc. of treatment	28 days after last dose	90 days after last dose	Every 12 weeks until death or for up to 2 years
Visit Window (days)	Within 28 d of first dose		± 2	± 3		± 3		± 7		± 2	± 7	± 7	± 7	± 7	± 14
Assessment		D1 C1	D8 C1	D1 C2		D1 C3		D1 C4		D15 C4					
Informed consent	X														
Review of eligibility criteria	X	X													
Medical history a	X														
NYHA class evaluation	X														
Tumor biopsies/archival tissue collection ^b	X					X									
12-lead ECG ^c	X	X		X								X	X	X	
Performance status (ECOG)	X	X		X		X		X			X	X	X	X	
Physical examination	X	X		X		X		X			X	X	X	X	
MRI or CT disease assessment by RECIST ^d	X					X				X	X d	X	X	X	
AGEN1884 administration ^e		X		X		X		X			X				
Serum chemistry f	X	X	X	X		X		X			X	X	X	X	
Endocrine function tests (free T4, TSH and ACTH) ^f	X	X	X	X		X		X			X		X		
Hematology f	X	X	X	X		X		X		•	X	X	X	X	
Tumor marker assessment g	X	X		X		X		X			X	X	X	X	
Urinalysis ^f	X	X	X	X		X	T	X			X	X	X	X	
Coagulation ^f	X	X	X	X		X		X			X	X	X	X	

Confidential Page 48 of 78

	Screening		Treatment and Evaluation									Disease Assessments	End of Treatment Visit	Final Safety Visit	Survival F/U		
Study Week		1	2		4			7			10	12	Q3, 6, and 12W after Week 12	After disc. of treatment	28 days after last dose	90 days after last dose	Every 12 weeks until death or for up to 2 years
Visit Window (days)	Within 28 d of first dose	l	± 2		± 3			± 3			± 7	± 2	± 7	± 7	± 7	± 7	± 14
Assessment		D1 C1	D8 C1		D1 C2			D1 C3			D1 C4	D15 C4					
Adverse events	X	X	X		X			X			X	X	X	X	X	X	
Pregnancy test h	X	X			X			X			X		X		X	X	
Concomitant medications	X	X	X		X			X			X	X	X	X	X	X	
Vital signs i	X	X i	X		X i			X^{i}			X i	X	X i	X	X	X	
Evaluation of DLTs (phase 1 dose escalation only)		X	X		X												
PGx (whole blood) j	X																
Blood sample for serum PK and/or ADA k		X	X		X			X			X	X			X	X	
Survival follow-up and initiation of subsequent therapy																	X

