5.8.4 Clinical Laboratory Assessments

Blood samples will be collected and submitted to the institution's local laboratory according to the institution's standard procedures.

Standard laboratory procedures and institutional guidelines will be followed to analyze and report findings for hematology, coagulation times, and serum biochemistry.

Normal ranges with the units of measure for all required parameters will be provided to the study sponsor by the local laboratory conducting the clinical laboratory analysis. All results may be reported in conventional units if this is the typical clinic report method for the local laboratory; otherwise, the International System of units may be used.

A listing of clinical laboratory assessments to be performed is provided in Table 12.

Confidential Page 56 of 78

Table 12: Clinical Laboratory Assessments

Hematology	Red blood cell count Platelets Hematocrit Hemoglobin WBC count	WBC differentials and absolute counts: Neutrophils Eosinophils Basophils Lymphocytes Monocytes				
Serum biochemistry	Albumin Alkaline phosphatase Aspartate amino transferase Alanine amino transferase Total bilirubin Blood urea nitrogen Glucose	Creatinine Potassium Sodium Lactate dehydrogenase				
Endocrine function tests	Free thyroxine (T4) Thyroid-stimulating hormone Adrenocorticotropic hormone					
Urinalysis	Red blood cells WBCs Protein					
Coagulation	Prothrombin time INR Partial thromboplastin time					
Tumor markers	Tumors with known markers, such as alpha-fetoprotein for HCC and cancer antigen 125 for ovarian cancer					
Other	Serum and urine pregnancy tests (for women of childbearing potential only) PGx					

HCC: hepatocellular carcinoma; INR: International Normalized Ratio; PGx: pharmacogenomics; WBC: white blood cell.

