5.8.6.1.2 Immune-Related Adverse Events

Blocking CTLA-4 function may permit the emergence of immune-mediated AEs that result in clinical syndromes resembling autoimmunity. Rash/vitiligo, diarrhea/colitis, uveitis/episcleritis, hepatitis, and hypopituitarism were drug-related, presumptive immune-related events noted in previous studies of anti–CTLA-4 agents.

For the purposes of this study, an irAE is defined as an adverse event of unknown etiology, associated with drug exposure, and is consistent with an immune phenomenon. Efforts should be made to rule out neoplastic, infectious, metabolic, toxin, or other etiologic causes prior to labeling an adverse event an irAE. Serological, immunological, and histological (biopsy) data should be used to support the diagnosis of an immune-mediated toxicity.

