6.5 Analysis Visit Window

Data will be analyzed by scheduled visits, where appropriate. Data collected out of the prescribed timing window will be analyzed as scheduled (i.e., at intended visits). Data that are collected from an unscheduled visit will not be included in the by-visit summary tables but will be presented in the listings. However, data collected at an unscheduled visit will also be considered for toxicity grading, in particular, for laboratory assessments. Additionally, both unscheduled and out of window imaging assessments will be included in the efficacy analysis.

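### SAP 8.6.4 plans no grading, worst-value shift table or subject count for TSH, free T4 and ACTH, although they are drawn at every dosing visit

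*SAP*

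**What the plan says.** **Collection.** Protocol 5.1 (Table 10) schedules free T4, TSH and ACTH at screening, Cycle 1 Days 1 and 8, Day 1 of Cycles 2 to 4, and the visits after Week 12. Protocol 5.8.4 (Table 12) gives the panel its own row: "Free thyroxine (T4) Thyroid-stimulating hormone Adrenocorticotropic hormone".

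**Known harm.** Protocol 5.8.6.1.2 says of earlier agents in this class: "hepatitis, and hypopituitarism were drug-related, presumptive immune-related events noted in previous studies". Laboratory evaluation is part of the primary safety endpoint (Protocol 6.2; SAP 4.4).

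**Protocol limits.** Table 7 in Protocol 4.3.5 has a row for an asymptomatic TSH abnormality with numerical limits: "If TSH <0.5 x lower limit of normal (LLN) or TSH >2 x ULN".

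**Analysis.** For laboratory parameters in general, SAP 8.6.4 states that "descriptive summary tables for observed values and changes from baseline will be provided by visit". SAP 8.1 defines the statistics as n, mean, SD, median, minimum and maximum. Toxicity grading is listed for eight parameters only: "ALT, AST, Bilirubin, Creatinine, Hemoglobin, Platelets, Neutrophils, and Lymphocytes". The shift tables run from baseline toxicity grade to the worst post-baseline value, scheduled or not.

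**Unscheduled values.** SAP 6.5: "Data that are collected from an unscheduled visit will not be included in the by-visit summary tables but will be presented in the listings". The same section readmits such values for toxicity grading.

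**Other summaries.** SAP 8.6.2 adds a summary of laboratory abnormalities that worsen by CTCAE v5 in at least one on-study measurement, without naming parameters. It also reports adverse-event clusters for thyroid, pituitary and adrenal conditions.

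**The concern.** A safety table for a monitored laboratory test should answer one question: how many subjects became abnormal, and in which direction. For the eight graded parameters the shift table answers it. For the endocrine panel nothing in SAP 8.6.4 does.

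The by-visit statistics suit this panel poorly. The SAP's own clusters include both hypothyroidism and hyperthyroidism, so values can move either way and partly offset in a mean. A median does not move when a minority changes. An abnormal value seen only at an unscheduled visit is left out of these tables altogether.

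Adverse-event reporting closes only part of the gap. Under Protocol 5.8.6.2.1 a laboratory change must be recorded as an adverse event only if the investigator considers it clinically significant. Abnormal values that are not so judged are left to the listings and to pooled by-visit statistics. At stake is the completeness of one component of the primary safety description, for a harm the protocol names in advance.

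**Working it through.** The documents state no figure on this point, so there is none to reproduce. The check sets the sections side by side and then illustrates what the planned statistics can and cannot show.

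**1. Where an endocrine value can appear**

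| Planned output | Endocrine panel included? | Unscheduled values? | Counts subjects? |
|---|---|---|---|
| By-visit descriptive tables (SAP 8.6.4, 8.1) | Yes | No (SAP 6.5) | No |
| CTCAE grading and grade-shift tables (SAP 8.6.4) | No, eight other parameters | Yes | Yes |
| CTCAE worsening summary (SAP 8.6.2) | Not stated | Any on-study measurement | Not stated for these tests |
| AE, irAE and cluster tables (SAP 8.6.2) | Only once reported as an adverse event | Not applicable | Yes |
| Laboratory listing (SAP 8.6.4, 6.5) | Yes | Yes | No |

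Whether CTCAE v5 grades TSH, free T4 or ACTH cannot be settled from the documents, so the third row stays open. The endocrine clusters are built from diagnosis terms such as hypothyroidism or adrenal insufficiency. They list no laboratory-result term, so a TSH abnormality coded as a laboratory finding would not enter them.

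**2. The SAP counts threshold crossings elsewhere.** It counts ALT, AST or bilirubin normal at baseline and then at least 2 x ULN (8.6.2). It also counts subjects beyond limits for QTcF, heart rate, PR and QRS (8.6.6). TSH has explicit limits in Protocol Table 7 but no matching count.

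**3. Illustration.** Only N = 60, the Phase 2 maximum (SAP 3.2), comes from the documents. Assumed: TSH 2.0 at baseline in everyone, LLN 0.4 and ULN 4.0, so that the Table 7 limits are 0.5 x 0.4 = 0.2 and 2 x 4.0 = 8.0; free T4 15 at baseline. Mean change = sum of changes / 60.

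| Case | Mean change | Median | SD | Range of change | Subjects shifted |
|---|---|---|---|---|---|
| A: TSH, 1 rises to 15, 7 fall to 0.1 | (13 - 7 x 1.9)/60 = -0.005 | 0 | 1.81 | -1.90 to +13.00 | 8/60 = 13.3% |
| B: TSH, 3 rise to 12, 15 fall to 0.1 | (3 x 10 - 15 x 1.9)/60 = +0.025 | 0 | 2.45 | -1.90 to +10.00 | 18/60 = 30.0% |
| C: TSH, 6 rise to 10, 6 fall to 0.1 | (6 x 8 - 6 x 1.9)/60 = +0.61 | 0 | 2.55 | -1.90 to +8.00 | 12/60 = 20.0% |
| D: free T4, 6 fall to 7, 6 rise to 23 | (6 x 8 - 6 x 8)/60 = 0 | 0 | 3.61 | -8 to +8 | 12/60 = 20.0% |

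In A to C every shifted subject is beyond the assumed Table 7 limits.

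- Means can mask two-sided change (A, B, D), but not always. In C equal numbers of rises and falls leave a mean of +0.61, because a fall in TSH is bounded at zero.
- The minimum and maximum reveal that extremes exist. They do not give the number: the observed TSH minimum is 0.1 in A, B and C, with 7, 15 and 6 low subjects respectively.
- Samples go to local laboratories with their own normal ranges (Protocol 5.8.4), so a pooled minimum or maximum cannot be read against a single LLN or ULN.

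**4. What a count would add.** For x of n, the Wilson 95% interval is (p + z²/2n ± z√[p(1-p)/n + z²/4n²]) / (1 + z²/n). For 8/60: (0.1333 + 0.0320 ± 1.96 x 0.0468)/1.0640 = 6.9% to 24.2%. For 12/60: 11.8% to 31.8%. For 18/60: 19.9% to 42.5%.

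**The case against.** The strongest case against has four parts.

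- **The by-visit tables hold more than mean changes.** They give observed values, SD, minimum and maximum, and the last two do not cancel. In case A the table would show changes from -1.90 to +13.00. This stands, so masking applies to the mean and median only.
- **SAP 8.6.2 may already cover these tests.** Its CTCAE worsening summary has no parameter list, and SAP 6.5 admits unscheduled values to grading. This stands as an uncertainty, since the only list of graded parameters in the SAP is the eight in 8.6.4. The SAP should state the scope.
- **Recognised endocrine disease is well reported.** Clinically significant changes must be recorded as adverse events. The thyroid, hypophysitis and adrenal clusters cover grade, hormone or steroid treatment, onset and duration over 90 days after the last dose. This stands and limits the gap to values not judged clinically significant.
- **The rest is listed.** With up to 60 subjects and no inferential aim, a reader could count from the listing. That is possible, but it leaves a simple incidence to be worked out by hand.

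A reader might also infer from Table 7 that repeat draws at 1 to 3 weeks for suspected endocrinopathy drop out of every table. The documents do not support that. The instruction belongs to the symptomatic row, where the event can reach the adverse-event tables. For an asymptomatic TSH abnormality, Table 7 places the added free T4 at subsequent cycles.

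**Conclusion.** The omission is real and its effect is modest. In SAP 8.6.4 the endocrine panel has no grading, no worst-value shift table and no subject count, and its by-visit tables exclude unscheduled values. Abnormal values not judged clinically significant may therefore be visible only in listings or inside pooled by-visit statistics.

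A reader might infer more: that only mean changes are tabulated, or that endocrine toxicity could disappear from the report. Neither follows. The tables include the extremes, and recognised toxicity is summarised through the AE, irAE and cluster tables.

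The number of subjects affected is unknown. The 13.3% to 30.0% in the working rests on assumed values and shows only that the planned statistics do not convey a count. The conclusion also assumes that the grade-shift tables are confined to the eight graded parameters, which is the plain reading of 8.6.4. If the 8.6.2 summary is meant to include these three tests, the gap narrows further. No estimate or decision rule in the plan changes. Severity: minor improvement.

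**What to change.** In SAP 8.6.4:

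1. For TSH, free T4 and ACTH, add shift tables in low/normal/high categories, using the local normal range, from baseline to the lowest and to the highest post-baseline value, scheduled or unscheduled.
2. Add the number and percentage of subjects whose TSH is ever below 0.5 x LLN or above 2 x ULN. These limits are taken from Protocol Table 7 for tabulation only and imply no change to patient management. Report the count overall and in the SAP's three existing subgroups: HCC; non-HCC and PD-1/PD-L1 refractory; non-HCC and PD-1/PD-L1 naïve.

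In SAP 8.6.2, state whether the summary of worsening laboratory abnormalities covers these three tests.

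The cost is one or two extra tables and a sentence. The tests are already collected, and SAP 8.6.4 already provides for normal ranges and above- and below-normal flags, so no new data are needed.

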8.6.5 Body Weight and Vital Signs

The observed value and percentage of changes from baseline will be summarized and listed by visit for Safety Analysis Set. If there are multiple measurements per visit, these measurements will be averaged.

Mean values of body weight, with 95% confidence interval will be plotted by each scheduled visit.

Listing will be provided for Safety Analysis Set.

8.6.6 12-lead Electrocardiogram

Number of subjects with abnormal clinically not significant and abnormal clinically significant electrocardiogram (ECG) results, as well as number of subjects with QTc_F (QT interval corrected using Fridericia's formula) greater than 450 or 480milliseconds will be summarized by visit and timing with respect to drug dose. In addition, QTc_F changes from pre-dose will be summarized for number of patients with a change exceeding a threshold of 30 msec or 60 msec. In these summaries, QTc intervals will be averaged for ECG taken in triplicate.

Other ECG parameters will be reported and summarized. Hart rate (HR) will be summarized as for number of patients \leq 50 bpm and \geq 120 bpm, PR interval for number of patients with PR \geq 220 msec, and duration of QRS complex for number of patients with QRS \geq 120 msec.

In all these summaries, QT, PR, QRS durations, and HR will be averaged for ECG taken in triplicate.

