4.2 Infusion Reactions

Subjects receiving AGEN1884 should be monitored for infusion reactions. This includes the measurement of vital signs for ≥1 hour after infusion, defined as 1 hour after the completion of the 60-minute infusion of AGEN1884 and the 15-minute flush that follows the infusion. Subjects will remain in the clinic under close supervision for the duration of this monitoring period. Subjects with mild or moderate infusion reactions may receive AGEN1884 with close monitoring. Premedication with an antipyretic or antihistamine may be considered. For severe infusion reactions, AGEN1884 infusion must be discontinued, and appropriate medical therapy should be administered.

Subjects who do not experience any grade ≥ 1 infusion-related toxicity during or after the infusion may be released from monitoring after 1 hour if they are otherwise stable. Subjects with any infusion-related toxicity must be managed as per the guidelines below, and monitoring will continue until any infusion-related toxicity has abated to grade <1 and ≥ 1 hour has passed from the completion of the entire infusion and flush. Before leaving the study site, all subjects will be given information on infusion-related toxicity per institutional guidelines. This will include instructions on when and how to return for immune-mediated toxicities associated with CTLA-4 blockade.

If mild or moderate infusion reaction occurs, the infusion should be interrupted, and supportive care should be administered until the symptoms resolve, per treating clinician.

Management guidelines for infusion reactions will be provided to the investigators at each site (Table 2).

Confidential Page 35 of 78

Table 2: Infusion Reaction Guidelines

CTCAE Grade	Treatment	Premedication at Subsequent Dose Administration
Grade 1 Mild reaction; infusion interruption not indicated; intervention not indicated.	Increase monitoring of vital signs as medically indicated until the subject is deemed medically stable in the opinion of the investigator.	None.

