5.8.2 Vital Signs

Vital signs will be measured at all visits indicated in the schedule of assessments (Table 10) and documented in the medical record. Measurements to be reported are temperature in Celsius or Fahrenheit, pulse (beats per minute), respiratory rate (breaths per minute), oxygen saturation, and blood pressure.

Vital sign measurements will be collected within 30 minutes prior to study drug administration, and every 30 (\pm 10) minutes during the 60-minute AGEN1884 infusion, including at the end of the 15-minute flush of the infusion line (\pm 15 minutes). This would equate to 4 sets of vitals over the course of a 60-minute infusion and flush, including the pre-administration vitals. A final set of vitals will be collected 1 hour (\pm 15 minutes) following the flush of the infusion line, unless otherwise indicated.

Because AGEN1884 is administered based on subject body weight, weight will be collected before each dose of AGEN1884 to confirm the administered dose. The subject's weight at the Week 1 (Cycle 1, Day 1) visit should be used for dosing calculations unless there is a >10% change in body weight. Dose adjustments for each cycle are only needed for a >10% change in weight.

5.8.3 12-Lead Electrocardiogram

A 12-lead ECG will be recorded as indicated in the schedule of assessments (Table 10). The corrected QT (QTc) interval will be calculated using Fridericia's formula.

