4.4 Primary Endpoints

- Safety and tolerability will be assessed by monitoring the frequency, duration, and severity of drug-related adverse events; by completing physical examinations; by evaluating changes in vital signs and electrocardiogram (ECG); through clinical evaluations; and laboratory blood and urine sample evaluations.
- PK parameters to be estimated and reported may include, but may not be limited to, maximum drug concentration at steady-state (C_{max-ss}), minimum drug concentration at steady state (C_{min-ss}), area under the drug concentration-time curve within time span t1 to t2 at steady-state (AUC_{(t1-t2)-ss}), area under the drug concentration-time curve from time of dosing to time of last observation (AUC_(0-t)), area under the drug concentration-time curve

from time of dosing extrapolated to infinity (AUC_(0- ∞)), time to reach maximum drug concentration (t_{max}), terminal elimination rate constant (λ_z), terminal elimination half-life (t½), systemic clearance (CL), and volume of distribution (Vd).

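### SAP 8.6.5 averages five timed vital-sign sets per dosing visit, so its by-visit table dilutes a brief infusion-day change and cannot separate it from a between-visit change

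*SAP*

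**What the plan says.** **Collection.** Protocol 5.8.2 arranges dosing-day vital signs around the infusion. One set comes before it: "Vital sign measurements will be collected within 30 minutes prior to study drug administration". More follow at roughly half-hour steps to the end of the flush, and the section gives the total: "This would equate to 4 sets of vitals over the course of a 60-minute infusion and flush, including the pre-administration vitals". It then adds another: "A final set of vitals will be collected 1 hour" after the flush, with a 15-minute window. The vital-signs footnote to Table 10 repeats the scheme. Protocol 4.2 gives the purpose: "Subjects receiving AGEN1884 should be monitored for infusion reactions". It continues: "This includes the measurement of vital signs for ≥1 hour after infusion".

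**Analysis.** SAP 8.6.5 states: "The observed value and percentage of changes from baseline will be summarized and listed by visit for Safety Analysis Set". The next sentence is the rule at issue: "If there are multiple measurements per visit, these measurements will be averaged". The section has no breakdown by time within the visit, no worst-value summary and no threshold count for vital signs.

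**Status.** SAP 4.4 names change in vital signs as one element of the primary safety endpoint. Under SAP 6.1, baseline is the last available value before first dosing.

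**The concern.** The five sets are not replicates. They are taken under different conditions (undosed, dosing, recovery), and the contrast between those conditions is the reason for taking them. Averaging removes that contrast before any change is computed.

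What is at stake is the one planned summary of *measured* vital signs. The adverse-event tables rest on what investigators judged and reported. The vital-sign table is the check on that judgement from the data themselves. A short fall in blood pressure or oxygen saturation, or a brief fever, could leave only a small trace in it.

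**Working it through.** **1. Number of readings.** From Protocol 5.8.2: pre-dose, about 30 min, about 60 min, end of flush = 4, which reproduces the protocol's own count. Adding the set one hour after the flush gives 5.

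**2. Dilution.** Let the pre-dose value be P, and let k of the 5 readings shift by D. The visit average is [(5 − k)P + k(P + D)]/5 = P + kD/5. With an assumed fall of 30 mmHg (not from the documents):

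| Readings shifted (k) | Share kept (k/5) | Fall seen in visit average |
|---|---|---|
| 1 | 20% | 6 mmHg |
| 2 | 40% | 12 mmHg |
| 3 | 60% | 18 mmHg |
| 4 (all after pre-dose) | 80% | 24 mmHg |

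**3. An uneven profile.** Assumed systolic readings 130, 128, 90, 115, 127:
- Average = 590/5 = 118.
- Change in the average = 118/130 − 1 = −9.2%.
- Change at the lowest reading = 90/130 − 1 = −30.8%.
- A 40 mmHg fall therefore appears as 12 mmHg.

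**4. Cancellation.** Shifts of 0, +20, +20, −20, −20 from pre-dose average to 0/5 = 0.

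**5. Acute against between-visit change.** A visit average 6 mmHg below baseline arises if one reading falls by 30 (30/5 = 6), or if all five readings, pre-dose included, are 6 lower than at baseline. The averaged table gives the same entry for both.

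**6. Cycle 1 Day 1.** If the pre-dose set of that day is the baseline under SAP 6.1, its change from baseline is zero by construction. With later shifts d1 to d4, the tabulated change is (0 + d1 + d2 + d3 + d4)/5, which is 4/5 of the mean of the four later changes.

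**7. Group mean.** Assume 10% of subjects have the 30 mmHg fall. The mean of visit averages moves by 30 × 0.10 × k/5, which is 0.6 mmHg for k = 1 and 2.4 mmHg for k = 4. At an affected time point it moves by 30 × 0.10 = 3.0 mmHg.

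**8. Temperature (secondary).** Protocol 5.8.2 accepts either scale, and percentage change depends on the scale. From 37.0 to 39.0 °C is 2.0/37.0 = 5.4%. The same rise, 98.6 to 102.2 °F, is 3.6/98.6 = 3.7%.

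**The case against.** **The sentence may mean replicates only.** This is the most favourable reading, but the wording is per visit. Where the SAP means replicates it says so: 8.6.1 averages weights only within a time point, and 8.6.6 averages triplicate ECGs. Section 8.6.6 also keeps the timing of ECGs relative to dosing, while 8.6.4 and 8.6.8 use worst values for graded laboratory tests and for ECOG status. Vital signs have none of these protections, so the text needs correcting even if replicates were intended.

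**Infusion effects are reported elsewhere.** This stands, and it limits the point. SAP 8.6.1 counts doses and subjects with infusion-related reactions, and interrupted doses. SAP 8.6.2 makes infusion-related reactions events of special interest and tabulates them by term and grade. Protocol 5.8.6.2.1 requires a vital-sign change that the investigator judges clinically significant to be recorded as an adverse event. A reader might infer that the primary safety analysis as a whole cannot show an infusion-related change. The documents do not support that.

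**Real-time monitoring is unaffected, and no promise is broken.** Both are true. The averaging rule does not touch monitoring in the clinic, and Protocol 6.4.1 commits only to descriptive statistics of vital signs. The point concerns the quality of the table, not a departure from the protocol.

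**Longer-term drift can still be seen.** Also true. Table 10 schedules vital signs at visits with no infusion-day scheme, such as Cycle 1 Day 8, Cycle 4 Day 15, End of Treatment and Final Safety. The confusion of acute with between-visit change is limited to dosing visits.

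**A time-point mean can also hide one subject.** A 40 mmHg fall in one of 60 subjects moves a time-point mean by 40/60 = 0.7 mmHg. This stands, and is why a worst-change summary is needed as well as the split by time point.

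**A listing is planned.** The SAP does not say whether it shows individual or averaged readings, so it is not a sure backstop. Nor are the minimum and maximum in SAP 8.1, if they are computed on averages.

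**Conclusion.** The concern holds for the vital-sign summary. As written, SAP 8.6.5 reduces an infusion-day change to kD/5, between 20% and 80% of its size. It can cancel opposite changes, and at dosing visits it cannot separate an acute change from a between-visit one.

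It would go too far to say that the table cannot show any infusion-related change, since a shift sustained over all four later readings keeps 80%. It would also go too far to speak of a general five-fold dilution, which applies only when exactly one reading moves.

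The temperature point is secondary. The SAP states unit conversion only for laboratory tests, but nowhere says that mixed temperature units would be summarised unconverted.

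The fraction k/5 assumes that all five scheduled sets are recorded and equally weighted. Extra readings taken during a reaction would change the weights. The blood-pressure values and the 10% of subjects are illustrations, not trial data. The study is descriptive and not sized on inference, so no error rate or power is affected.

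**What to change.** In SAP 8.6.5:

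- Summarise vital signs by visit and nominal time point, with absolute change from the same-day pre-dose value and from baseline.
- Add the worst post-dose change from pre-dose per subject per visit: lowest systolic pressure and oxygen saturation, highest pulse and temperature.
- Average only replicates at the same time point, as 8.6.1 already does for weight.
- State that temperature is converted to one unit before summary.

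It would also help to say that the listing shows individual readings with their time points.

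The cost is SAP wording, some programming and a longer table. The protocol already schedules the readings, so nothing changes for sites or subjects.
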